2.3 Rationale

CPB is frequently used in cardiac surgery and canlead to ischemic, inflammatory and oxidative damage of renal tubular epithelial cells. However, the exact mechanism of renal tubular epithelial cell damage is still unknown. Although numerous studies have investigated different pharmacological interventions to prevent AKI, effective strategies are missing. The KDIGO guidelines for AKI recommend various non-interventional strategies for the prevention of AKI:

- Discontinuation of all nephrotoxic agents when possible
- Optimization of volume status and hemodynamic parameters including perfusion pressure
- Consideration of functional hemodynamic monitoring
- Close monitoring of serum creatinine and urine output
- Avoidance of hyperglycemia
- Consideration of alternatives to radio contrast agents
- Discontinuation of ACEi and ARBs

Although the evidence for the different supportive measures is weak, the KDIGO guidelines recommend to implement them in patients at high risk for AKI.

Therefore, a randomized prospective multicenter trial is needed to investigate whether the implementation of the bundle of measures is effective to prevent AKI in high risk patients undergoing cardiac surgery. In this feasibility trial we will analyze the compliance rate to the trial protocol in a multicenter, multinational cohort in preparation for a large randomized controlled trial.

CONFIDENTIAL

Date: 16.02.2017 Version: V1

2.4 Benefit-risk assessment

Patients included in the trial have an increased risk for the development of AKI.

In the validation group, the bundle of supportive measures recommended by the KDIGO guidelines will be implemented, whereas patients in the control group receive standard of care therapy. Cardiacoutput (e.g. measured by echocardiography; at initiation and then every 3h up to 12h) will be measured in both groups without informing the treating physician about the values. The intervention may reduce the occurrence and severity of AKI.

The KDIGO guidelines include optimization of volume status and hemodynamic parameters, discontinuation of nephrotoxic agents when possible, discontinuation of ACEi and ARBs, close monitoring of serum creatinine and urinary output, and avoidance of hyperglycemia. To this date, the benefit of these simple and uncomplicated measures has not been proven. Patients assigned to the control group will not have any disadvantages compared to non-participation in the study.

All the patients included in this trial receive standard therapy according to the current clinical routine at each center. The patient's primary physicians will determine the remainder of patient management consistent with established best practice within the institution.

Significance

The occurrence of AKI after cardiac surgery is associated with an increased risk of morbidity and mortality. The KDIGO guidelines recommend to implement various measures in high risk patients to prevent AKI. However, it has not been proven whether the implementation of these measures reduces the occurrence of AKI after cardiac surgery. Patients at high risk for AKI will be identified by using the AKI biomarkers [TIMP-2]*[IGFBP7] which will be measured 4h after cardiac surgery.

Given the fact that more than 2 million patients are scheduled for cardiac surgery each year worldwide, reducing the occurrence of AKI by biomarker-guided implementation of the KDIGO guidelines would result in a remarkable positive effect for many patients, health care systems and health economics.

To plan a large randomized outcome study, in which we investigate whether biomarker-guided implementation of the KDIGO guidelines can reduce the occurrence of AKI after cardiac surgery, we have to know the adherence to the trial protocol. Once we have these data, we can perform the power analysis for the outcome study.

CONFIDENTIAL

3 Organizational and administrative aspects of the trial

3.5 Investigators and trial sites

This clinical trial will be carried out as a multicenter trial with the University Hospital of Muenster as principal institution. The listing of trial sites, principal investigators, sub-investigators and further trial staff, will be kept and continuously updated in a separate list. The final version of this list will be attached to the final report of the clinical trial.

4 Trial conduct

4.1 General aspects of trial design

The clinical trial will be performed as a prospective, randomized controlled, blinded, parallelgroup, multicenter trial. Eligible patients will be randomized in a ratio of 1:1 to receive either interventional or standard treatment via an internet-based system.

Patients who are considered potential candidates for the study may only participate if signed written informed consent is provided or the specific process for unconscious patients in an emergency situation is followed before any study related procedures are initiated (see 4.3.1). Each consented patient will be assigned a unique patient number. This patient number will be used to identify the patient throughout the study. The patient's eligibility will be proven by checking the inclusion and exclusion criteria.

The randomization number allocates the patient to one of the treatment groups.

4.1.1 Time plan

The study comprises three main periods:

- Intervention period (from inclusion and randomization to 12 h)
- Observation period (during hospitalization)
- Follow-up period on day 90 after patient enrolment.

End of the clinical trial

The last patient's last visit (LPLV) is defined as the end of the clinical trial.

4.2 Discussion of trial design

All patients will receive standard perioperative care. In the validation group, patients will be strictly treated according to the KDIGO guidelines and according to a special algorithm to optimize

CONFIDENTIAL

Date: 16.02.2017 Version: V1

volume status and hemodynamic parameters. The KDIGO recommendations are safe and have no side effects. In the control group, patients will receive standard care.

AKI after cardiac surgery is associated with an increased morbidity and mortality. Numerous clinical trials tested differentpharmacologicaltreatments,however no agents have been demonstrated to be efficacious in clinical practice. In a preliminary study, we demonstrated that urinary [TIMP-2]*[IGFBP7] levels 4 hours after CPB showed good performance in predicting the development of AKI (AUC 0.81). Moreover, patients with a cut-off value ≥ 0.3 ((ng/ml)²/1000) were identified to have a high risk for AKI (5-times higher than [TIMP-2]*[IGFBP7] < 0.3; p< 0.001). Thus, preventing AKI after cardiac surgery would have a great impact on morbidity and mortality.

4.2.1 Randomization

Prior to being randomized into the study, patients will have:

- Signed a written informed consent
- Completed screening
- Met all designated inclusion criteria and have no exclusion criteria

Randomization assignment (in a 1:1 ratio to the two treatment arms) will be given only to those patients fulfillingthe inclusion and none of the exclusion criteria and providing informed consent. Randomization will be performed by using a web-based randomization system. After identifying a high risk patient (urinary [TIMP2]*[IGFBP7] ≥ 0.3, NephroCheck® Test), patients will be assigned to control or intervention group, whereas the intervention will be provided by research staff not involved in the care of patient.

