	Severity of AKI (according to the KDIGO guidelines)					
	 Renal recovery at days 30, 60 and 90 (renal recovery is defined as serum creatinine levels < 0.5 mg/dl higher than baseline serum creatinine) 					
	30-day, 60-day and 90-day mortality					
	Length of ICU stay					
	Length of hospital stay					
	Need and duration of renal replacement therapy					
	• RRT at days 30, 60, 90					
	 MAKE₃₀, MAKE₆₀ and MAKE₉₀ (major adverse kidney events consisting of mortality, dialysis dependency, persistent renal dysfunction (defined as serum creatinine ≥ 2x compared to baseline value) 					
	Determination of different biomarkers					
	 Assessment of safety: complications in particular those related to the implementation of the KDIGO guidelines will be 					
	documented. No side effects have been reported.					
Number of subjects	To be assessed for eligibility: n=1000					
	To be allocated to the trial: n=310					
	To be analyzed: n=280 (140/ treatment arm)					
Time plan	First patient first visit (FPFV): 01/06/2017					
	Last patients first visit (LPFV): 31/05/2018					
	Last patient last visit (LPLV): 01/08/2018					
	Final study report: 01/11/2018					
	7 mai stady roport. 01/11/2010					

CONFIDENTIAL

Date: 16.02.2017 Version: V1

Statistics	Power analysis
	The required sample size is n=280 patients in total. This sample size is
	determined as follows:
	Patients will be randomized in a 1:1 ratio to one of the two treatment
	arms (intervention versus control). Randomization serves to estimate the
	incidence of AKI as secondary outcome to generate pre-information in
	terms of a pilot study for an upcoming confirmatory trial.
	The primary endpoint of the PrevAKI-multicenter trial is the compliance
	rate (Primary outcome: KDIGO recommendations fulfilled at all time), i.e.
	the proportion of patients who are treated according to the trial protocol.
	In order to estimate the compliance rate, the two treatment groups will
	be pooled together. In the primary analysis the compliance rate across
	all study patients will be estimated along with a two-sided 95%
	confidence interval (CI).
	As the compliance rate cannot be quantified in advance, we pursue a
	worst case approach and assume a compliance rate of 50%. In this case
	the CI has maximal width. Based on this assumption, with a sample size
	of n=280 patients the calculated 95% CI according to Clopper-Pearson
	(Fleiss 2003) ranges from 44% to 56%. Therefore, in case of any

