4.6 Treatment

All patients will receive standard of care therapy. In the validation group, functional hemodynamic monitoring (according to the standard of each center), optimization of fluid status and hemodynamic parameters according to a specific algorithm (see Figure 1), avoidance of hyperglycemia, discontinuation of nephrotoxic drugs if possible, consideration of alternatives to radio contrast agents, discontinuation of ACEiand ARBs, and close monitoring of serum creatinine and urine output will be performed. Further concomitant medication will not be restricted.

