6.2 Sample size

The required sample size is n=280 patients in total. This sample size is determined as follows.

Patients will be randomized in a 1:1 ratio to one of the two treatment arms (intervention versus control). Randomization serves to estimate the incidence of AKI as secondary outcome to generate pre-information in terms of a pilot study for an upcoming confirmatory trial.

The primary endpoint of the PrevAKI-multicenter trial is the compliance rate, i.e. the proportion of patients who have been treated according to the trial protocol (KDIGO recommendations fulfilled at all time). In order to estimate the compliance rate, the two treatment groups will be pooled together. In the primary analysis the compliance rate across all study patients will be estimated along with a two-sided 95% confidence interval (CI).

As the compliance rate cannot be quantified in advance, we pursue a worst case approach and assume a compliance rate of 50%. In this case the CI has maximal width. Based on this assumption, with a sample size of n=280 patients the calculated 95% CI according to Clopper-Pearson (Fleiss 2003) ranges from 44% to 56%. Therefore, in case of any observed compliance rate apart from the worst-case scenario, the 95% CI is never wider than 56%-44%=12%. This corresponds to an estimation of the compliance rate with a precision of plus/minus 6%.

CONFIDENTIAL

Date: 16.02.2017 Version: V1

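### No blocking or stratification by centre is stated and the secondary tests ignore centre, so the between-arm AKI estimate is less precise than it could cheaply be

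*Combined protocol and SAP*

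**What the plan says.** Section 4.1: "Eligible patients will be randomized in a ratio of 1:1 to receive either interventional or standard treatment via an internet-based system". Section 4.2.1: "Randomization assignment (in a 1:1 ratio to the two treatment arms) will be given only to those patients" who are eligible and have consented, and "Randomization will be performed by using a web-based randomization system". Sections 6.1 and 6.2 repeat the ratio. No section names the method of sequence generation, blocks, strata or minimisation.

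Care is partly local. Section 2.4: "All the patients included in this trial receive standard therapy according to the current clinical routine at each center". Section 4.6.2 gives controls standard of care. In the validation arm, section 4.6 includes "functional hemodynamic monitoring (according to the standard of each center", alongside the bundle and haemodynamic algorithm that the protocol itself fixes in 4.6.1.

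The synopsis gives "To be allocated to the trial: n=310" and "To be analyzed: n=280 (140/ treatment arm" in brackets. Section 6.2 derives the 280 from the pooled compliance rate: "In the primary analysis the compliance rate across all study patients will be estimated along with a two-sided 95% confidence interval (CI". The same section says that randomisation is there for the secondary AKI estimate, as input to a later confirmatory trial. Section 6.3 analyses secondary endpoints with Fisher, chi-squared, t or Mann-Whitney tests. Centre appears neither in those tests nor among the example covariates of the AKI risk-factor model.

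**The concern.** In a multicentre, multinational trial with local background care, centre is a foreseeable source of variation in AKI risk. As written, the plan deals with it neither at allocation nor in analysis. If allocation is unrestricted, each centre's split is left to chance, and differences between centres pass into the between-arm AKI difference as noise. That difference is the stated reason for randomising, and it is meant to feed the design of the confirmatory trial. Stratification has to be set before the first patient; it cannot be added afterwards.

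**Working it through.** **Inputs from the documents.** 310 allocated, 280 analysed, 140 per arm (synopsis); pooled compliance of 50% (6.2); AKI rates of 55.1% and 71.7% from the earlier single-centre trial (2.2), used only for illustration.

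**Assumptions.** Unrestricted 1:1 allocation; number and size of centres (3.5 leaves the sites to a separate list); SD of AKI risk between centres of 10, 15 or 20 points; two-sided alpha of 0.05 for AKI, for which the documents give no power calculation.

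**1. The plan's own figure.** The Clopper-Pearson interval for 140/280 is 43.99% to 56.01%, a width of 12.02 points, so the stated 44% to 56% reproduces. It uses the pooled count, so the split between arms does not enter.

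**2. Overall balance.** Under Binomial(280, 0.5) the SD of an arm size is sqrt(280 × 0.25) = 8.4, with a 95% range of 124 to 156. Power for 71.7% against 55.1% is 82.6% at 140/140 and 81.9% to 82.2% at 124/156, a loss of under 1 point. With 310 allocated, the arms differ by 20 or more patients in 28% of trials, and both arms reach 140 before losses in 92%.

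**3. Balance within centres.** Let p be the chance that one centre splits 2:1 or worse. The chance for at least one of C centres is 1 − (1 − p)^C.

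| Assumed centres | p | At least one centre |
|---|---|---|
| 5 of 62 | 0.0071 | 1 − 0.9929^5 = about 4% |
| 12 of 26 | 0.0755 | 1 − 0.9245^12 = 61% |
| 20 of 15 | 0.302 | over 99% |

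**4. Variance of the AKI difference.**
- Sampling variance in squared percentage points: 10,000 × (0.551 × 0.449/140 + 0.717 × 0.283/140) = 17.67 + 14.49 = 32.2, so the SD is 5.67 points.
- Part due to centre imbalance: simulation over assumed centre sizes with 310 patients gives SDs of 1.1, 1.6 and 2.1 points for centre SDs of 10, 15 and 20. As shares of the variance: 1.21/32.2 = 3.8%, 2.56/32.2 = 8.0%, 4.41/32.2 = 13.7%.
- Check: 2s × sqrt((C − 1)/(C × N)), where s is the centre SD, with C = 12 and N = 310 gives 1.09, 1.63 and 2.18 points, or 3.7%, 8.3% and 14.7%. With N = 280, to match the sampling variance, the shares are 4.1%, 9.2% and 16.3%. The upper end is therefore approximate.

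**5. Is this share added to 5.67, or inside it?** Inside. The marginal rates already contain the variation between centres. Simulated simple allocation with an assumed 14 centres of 20 gives an SD of about 5.6 to 5.7 points and about 95% coverage at every centre SD, including zero.

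**6. Does stratified allocation alone show the gain?** No. In the same setting it lowers the true SD to about 5.5, 5.4 and 5.2 to 5.3 points (repeat runs differ slightly). The unadjusted standard error does not follow, and coverage of the nominal 95% interval drifts up to about 96%. The gain reaches the reported interval only if the analysis also uses centre.

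**The case against.** The best defence is that this is a reporting gap on a secondary estimate. Several stronger readings that a reader might infer do fail:

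- **That allocation is simple and unstratified.** The documents are silent. The web system may block or stratify without the protocol saying so, and every probability above depends on its not doing so.
- **That local routine determines treatment in both arms.** Section 4.6.1 fixes the bundle and one haemodynamic algorithm for the validation arm. Only background care, control care and the monitoring method are local.
- **That imbalance biases the AKI comparison or adds variance beyond the usual interval.** Step 5 shows neither.
- **That failing to secure 140 per arm matters.** The sample size is the pooled 280, a 124/156 split costs under 1 point of power, and blocking could not guarantee 140 analysed per arm because losses come after randomisation.
- **That small centres could not show whether they deliver the bundle.** The primary analysis is one rate across all patients; no estimate per centre is planned.

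It is also fair that the centre numbers and SDs are assumed, and that with a few large centres the imbalance is rare.

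What remains is that the method is unstated, centre is absent from the between-arm analysis, and precision is given up on the comparison that randomisation serves.

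**Conclusion.** The concern holds as a modest, inexpensive improvement to the secondary AKI estimate. If allocation is unrestricted, roughly 4% to 14% of the variance of the AKI difference is removable, for an assumed centre SD of 10 to 20 points and about a dozen centres. Marked imbalance in at least one centre ranges from about 4% of trials (5 centres of 62) to 61% (12 of 26) and higher with smaller centres. If the web system already stratifies, the allocation part reduces to saying so, but the unadjusted tests in 6.3 would still not report the gain. The documents do not support reading this as a flaw in the primary endpoint, in the validity of the usual interval or in the 140-per-arm figure.

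**What to change.** In 4.1 and 4.2.1, state: central web-based randomisation, 1:1, stratified by centre, in permuted blocks of randomly varying size, with block sizes not disclosed to sites. If the system already does this, describe it.

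In 6.3, state that the between-arm AKI comparison will be stratified by or adjusted for centre, for example with a Mantel-Haenszel risk difference and its 95% confidence interval. Without this second change, the first does not narrow the reported interval.

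The cost is one setting in the web system before the first patient and a sentence in each place. The downside is some predictability at the end of a block within a site, which varying and concealing the block size limits.

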4.2.2 Blinding

Study intervention will be performed by research staffnot involved in anesthesia, perioperative care, and endpoint assessment.In the control group, the independent research staff will carry out the hemodynamic evaluation so that the trial is still blinded. General anesthesia and perioperativecarewill be performed in all patients by an experienced anesthesia team. Thus, blinding concerns i) the individual patient, ii) investigators obtainingdata, follow-up visits and documentation, and iii) the endpoint committee. Group allocation will not be unfolded until final statistical analysis.

Intention-to-treat analysis will address attrition bias. To prevent publication bias in future metaanalyses, results are intended to be published irrespective of the outcome of the trial.

CONFIDENTIAL

Date: 16.02.2017 Version: V1

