4.6.1 Experimental intervention

Four hours after terminating CPB in the context of a cardiac surgery procedure, urinary [TIMP-2]*[IGFBP7] will be measured to identify patients at high risk for AKI. Patients with a value ≥ 0.3 will be randomized as follows to one of the two treatment arms.

CONFIDENTIAL

[figure not shown]
Date: 16.02.2017 Version: V1

The KDIGO guidelines for prevention of acute kidney injury will be strictly implemented:

- Discontinuation of all nephrotoxic agents if possible
- Discontinuation of ACE inhibitors and ARBs forthe first 48 hours after surgery
- Close monitoring of serum creatinine and urinary output
- Avoidance of hyperglycemia by close monitoring for the first 72 hours after surgery
- Consideration of alternatives to radio contrast agents
- Functional hemodynamic monitoring (according to the standard of each center, e.g. PICCO, PAC, TOE)
- Hemodynamic monitoring and optimization according to a hemodynamic algorithm (see Fig. 1)

Figure 1. Hemodynamic algorithm (validation arm)

CI, cardiac index; CO, cardiac output; MAP, mean arterial pressure; PLRT, passive leg raising test

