4.7.1.3 Visits in detail

	T1 Base- line	T2 ¹ OD, interve ntion time	T3 POD 1	T4 POD 2	T5 POD 3	T6 Dis- charge	T7 Follow- up ²
Inclusion and exclusion criteria	X						
Randomization	Х						
Demographic Data (age, gender, BMI)	Х						
Medical history(preexisting condition, premedication)	Х						
Operation data (type of surgery, CPB time, X-clamp time, transfusion)	X						
Respiratory parameter	Χ	Χ					
Hemodynamic parameters (MAP, HR, CVP, CI, CO)		X					
Laboratory parameter (lactate, hemoglobin, electrolytes)	X	X	Х	X	Х		
Renal parameter (BUN, creatinine, GFR, urine volume [ml/h], urinary output, fluid balance)	Х	X	X	Х	X	X	Х
Blood and urine samples	X	X					
AKI (severity, diagnosis by,		Χ	Х	Χ	Χ		

¹ After randomization to end of intervention (12h)

² d30, d60, d90

Date: 16.02.2017 Version: V1

CONFIDENTIA

transient/persistent, RRT dependency, RRT days)						
Scores (APACHE II, SOFA)	Х	Х	Х	Х		
Concomitant medication (vasopressors, radio contrast agents, diuretics, ACEi, ARBs)	Х	Х	Х	Х		
Renal recovery					Х	Х
Mortality						Х
Length of ICU and hospital stay						Х
Renal replacement therapy	Х	Х	Х	Х	Х	Х
MAKE						Х
Complications (myocardial infarction, cerebral ischemia, ICB, bleeding >300ml/hour, re-operation)	Х	Х	Х	Х	Х	Х

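### The protocol calls the trial blinded, data collectors included, but the masking step it describes does not support that claim for them, and the treating team's status is unclear

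*Combined protocol and SAP*

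**What the plan says.** Section 4.1 describes a "prospective, randomized controlled, blinded, parallelgroup, multicenter trial". The trial type in the synopsis does not use the word blinded.

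Section 4.2.2 says who is covered: "Thus, blinding concerns i) the individual patient, ii) investigators obtainingdata, follow-up visits and documentation, and iii) the endpoint committee". The treating team is not on that list. Two mechanisms are given. One is staffing: "Study intervention will be performed by research staffnot involved in anesthesia, perioperative care, and endpoint assessment". The other is the matched procedure in controls: "In the control group, the independent research staff will carry out the hemodynamic evaluation so that the trial is still blinded". The section adds: "Group allocation will not be unfolded until final statistical analysis".

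The bundle in 4.6.1 is wider than hemodynamics. It includes "Discontinuation of ACE inhibitors and ARBs forthe first 48 hours after surgery", close glucose monitoring for 72 hours after surgery, stopping nephrotoxic agents where possible, considering alternatives to contrast, and optimization by an algorithm. The visit table in 4.7.1.3 has the sites record "Concomitant medication (vasopressors, radio contrast agents, diuretics, ACEi, ARBs"), together with MAP, CI and CO. Section 4.8 makes the responsible investigator the person who documents all trial data, with delegation allowed within the trial team.

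**The concern.** A blinding claim has to rest on something that stops the named person from learning the arm. For the data collectors, the protocol gives a matched measurement and nothing more. They also handle the record of treatments that the bundle is meant to change, and no text separates that record from the recording of AKI.

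The primary compliance estimate is not what is at stake. Section 6.2 says that randomization is there to estimate AKI incidence as input to a confirmatory trial. If readers take that comparison as protected by blinding, they will give it more weight than the procedures justify. AKI by urine output is the more exposed part: section 2.2 itself says that urinary output depends on diuretics and fluid status and has low specificity. RRT start and length of ICU or hospital stay depend on clinical decisions, and the masking of the people who make them is not stated.

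**Working it through.** **1. The plan's own figure.** Section 6.2 gives a Clopper-Pearson interval of 44% to 56% for 50% compliance and n=280. With x=140:

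- lower limit = 2.5% quantile of Beta(140, 141) = 43.99%
- upper limit = 97.5% quantile of Beta(141, 140) = 56.01%
- width = 56.01 − 43.99 = 12.02 points

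The figure reproduces. Nothing in it depends on masking.

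**2. Bundle items (4.6.1) against masking and recording.**

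| Item | Matched in controls? | Stated duration | In the readable visit table (4.7.1.3)? |
|---|---|---|---|
| Stop nephrotoxic agents | Not described | None | Not listed as such |
| Stop ACEi/ARB | Not described | 48 h after surgery | Yes |
| Creatinine and urine output | Schedule does not distinguish arms | None | Yes |
| Avoid hyperglycemia | Not described | 72 h after surgery | Glucose not listed |
| Contrast alternatives | Not described | None | Contrast use: yes |
| Functional hemodynamic monitoring | Cardiac output is measured (4.6.2) | None | CI, CO: yes |
| Hemodynamic monitoring and optimization | Measurement only, not the optimization | None | MAP, CI, CO: yes |

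So the matched procedure covers the measuring content of two items, and a common schedule covers a third. For the optimization and the remaining four items, no masking is described.

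**3. Duration.** The intervention period is 12 h from randomization (4.1.1, 4.4.1). The biomarker is measured 4 h after CPB. Assume that randomization follows at once and that surgery ends with CPB. The period then ends at 4 + 12 = 16 h, and ACEi/ARB withdrawal runs 48 − 16 = 32 h longer and glucose monitoring 72 − 16 = 56 h longer. Later randomization shortens both gaps hour for hour. In that time the primary physicians run the care outside the bundle (4.6.3), and the protocol does not say how staff outside patient care (4.2.1) keep these items in place without others seeing it.

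**4. Masking by role.**

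- *Patient:* section 4.3.1 says most are sedated and ventilated on ICU arrival, so masking at the start is plausible.
- *Endpoint committee:* can be masked if it receives only outcome data. The readable text does not say what it receives; some sections were not available to this review, so this is not held against the plan.
- *Data collectors:* claimed as blinded. They record ACEi, ARBs, vasopressors, contrast, CI and CO, and the same visit table has AKI severity as an entry.
- *Treating team:* not claimed in 4.2.2, but covered by the unqualified label in 4.1.

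**5. Conflicting text.** Section 2.4 says that cardiac output is withheld from the treating physician in both groups. The synopsis and 4.6.2 say this of controls only.

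**6. A scale, not an estimate.** The documents give no rate of unmasking and no misclassification rate. As a pure assumption, let knowledge of the arm lower recorded AKI in the intervention arm by d points with no true effect, at the single-center control rate of 71.7% (2.2) and 140 per arm. The single-center difference was 71.7 − 55.1 = 16.6 points. The chance of a false significant benefit, by the normal approximation, is Φ[(d − 1.96·√(2p̄(1−p̄)/140)) / √((p₁(1−p₁)+p₂(1−p₂))/140)], with p₁ = 0.717, p₂ = p₁ − d and p̄ their mean.

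| Assumed d | d / 16.6 | Chance of false benefit (nominal 2.5%) |
|---|---|---|
| 2 points | 12% | 5.6% |
| 5 points | 30% | 14.6% |
| 10 points | 60% | 42.6% |

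This shows how sensitive the comparison would be. It does not show that any of these shifts occurs.

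**The case against.** The strongest reply is that the protocol does have masking where it counts. Intervention staff are kept out of endpoint assessment, an endpoint committee is named as blinded, and the patients are mostly sedated. AKI rests partly on laboratory creatinine, and it is a secondary outcome of a feasibility trial. Most of this stands, and it limits the point to data collectors and the treating team.

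A reader might infer more than the documents support:

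- *That no blinding exists.* Nothing refutes masking of the patient at the start or of the endpoint committee.
- *That the whole bundle runs for 72 h.* Only glucose monitoring has that duration. ACEi/ARB withdrawal is 48 h, the formal intervention period is 12 h, and stopping nephrotoxic agents has no stated duration.
- *That the recorded drugs reveal the arm.* They can suggest it. Diuretics are not a bundle item. Other concomitant medication is unrestricted (4.6), so controls may also have ACEi/ARB withheld or receive vasopressors, and no control-arm rates are given.
- *That scoring compliance must break the blind.* This depends on whether compliance is judged per arm. Section 6.2 states one pooled criterion, and that ambiguity belongs to the endpoint definition.
- *That AKI is biased by a known amount.* The shifts in step 6 are assumptions.

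It is also fair to say that treating clinicians are not on the list in 4.2.2. Their view of the bundle conflicts with the label in 4.1, not with that list.

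**Conclusion.** The unqualified word blinded in 4.1, and its extension in 4.2.2 to investigators who obtain and document data, are not supported by the procedures described. The matched hemodynamic evaluation leaves most of the bundle unmasked. Two items outlast the intervention period, and the data collectors record variables that can suggest the arm. The treating team's status is unclear, because the cardiac output statements conflict.

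The conclusion rests on a comparison of the protocol's own sections, and on the absence, in the readable text, of any separation between treatment recording and outcome recording. The size of any bias in the AKI comparison cannot be estimated from the documents. The primary analysis, the sample size of 280 and the 44–56% interval do not change.

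**What to change.** 1. In 4.1 and 4.2.2, replace the unqualified word with a statement of masking for each role. Claim masking only where a mechanism exists, which on the present text means the patient and the endpoint committee.
2. Reconcile section 2.4 with the synopsis and 4.6.2 on when cardiac output is withheld from the treating physician, and state the treating team's status to match.
3. Derive AKI by program from dated creatinine and urine output, with arm and medication fields hidden. Give the endpoint committee those data plus RRT, and nothing else.
4. Use existing staff to keep compliance scoring separate from AKI classification.
5. Report creatinine-only AKI as a sensitivity analysis beside the full KDIGO definition.
6. Label RRT start and length of stay as outcomes decided by clinicians who are not shown to be masked.

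The cost is protocol wording, an assignment of roles, one derivation program and one extra analysis. The design claim becomes less favourable. Steps 3 to 5 limit biased classification; they do not remove the effect of different co-treatment by a team that is aware of the arm, which is why step 6 is needed.
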